Do not reservise. Do not use if package is demaged or open. Do not use after
the easily date printed on the sterile package. After removal the Neo-Sair
T CLJ 380 / Neo-Sair T CLJ 380 / Neo-Sair
T CLJ 380 / Neo-Sair
T CLJ 380 / Neo-Sair
T CLJ 380 / Neo-Sair
T CLJ 380 / Neo-Sair
T CLJ 380 / Neo-Sair
T CLJ 380 / Neo-Sair
T CLJ 380 / Neo-Sair
T CLJ 380 / Neo-Sair
T CLJ 380 / Neo-Sair
T CLJ 380 / Neo-Sair
T CLJ 380 / Neo-Sair
T CLJ 380 / Neo-Sair
T CLJ 380 / Neo-Sair
T CLJ 380 / Neo-Sair
T CLJ 380 / Neo-Sair
T CLJ 380 / Neo-Sair
T CLJ 380 / Neo-Sair
T CLJ 380 / Neo-Sair
T CLJ 380 / Neo-Sair
T CLJ 380 / Neo-Sair
T CLJ 380 / Neo-Sair
T CLJ 380 / Neo-Sair
T CLJ 380 / Neo-Sair
T CLJ 380 / Neo-Sair
T CLJ 380 / Neo-Sair
T CLJ 380 / Neo-Sair
T CLJ 380 / Neo-Sair
T CLJ 380 / Neo-Sair
T CLJ 380 / Neo-Sair
T CLJ 380 / Neo-Sair
T CLJ 380 / Neo-Sair
T CLJ 380 / Neo-Sair
T CLJ 380 / Neo-Sair
T CLJ 380 / Neo-Sair
T CLJ 380 / Neo-Sair
T CLJ 380 / Neo-Sair
T CLJ 380 / Neo-Sair
T CLJ 380 / Neo-Sair
T CLJ 380 / Neo-Sair
T CLJ 380 / Neo-Sair
T CLJ 380 / Neo-Sair
T CLJ 380 / Neo-Sair
T CLJ 380 / Neo-Sair
T CLJ 380 / Neo-Sair
T CLJ 380 / Neo-Sair
T CLJ 380 / Neo-Sair
T CLJ 380 / Neo-Sair
T CLJ 380 / Neo-Sair
T CLJ 380 / Neo-Sair
T CLJ 380 / Neo-Sair
T CLJ 380 / Neo-Sair
T CLJ 380 / Neo-Sair
T CLJ 380 / Neo-Sair
T CLJ 380 / Neo-Sair
T CLJ 380 / Neo-Sair
T CLJ 380 / Neo-Sair
T CLJ 380 / Neo-Sair
T CLJ 380 / Neo-Sair
T CLJ 380 / Neo-Sair
T CLJ 380 / Neo-Sair
T CLJ 380 / Neo-Sair
T CLJ 380 / Neo-Sair
T CLJ 380 / Neo-Sair
T CLJ 380 / Neo-Sair
T CLJ 380 / Neo-Sair
T CLJ 380 / Neo-Sair
T CLJ 380 / Neo-Sair
T CLJ 380 / Neo-Sair
T CLJ 380 / Neo-Sair
T CLJ 380 / Neo-Sair
T CLJ 380 / Neo-Sair
T CLJ 380 / Neo-Sair
T CLJ 380

Shelf-life: Four years.

Storage: Store in a dry place, below 30°C. Protect from direct sunlight and

Content: Copper, Polyethylene, Barium Sulphate, Polyamide 6.

incompatibilities: No known incompatibilities.

Nature and contents of container. The device with accessories packed in a heat sealed stenlised pouch made of Tyvek + PET/PE.

Date of first authorization: 25.05.2003 Date of last renewal: 31.07.2014

Date of revision of the text: 11.2014

Neo-Safe® T CU 380 Neo-Safe® T CU 380 Mini

## INFORMATION FOR THE USER

Design and dimensions. The Neo-Safe' T CU 380 Intrauterine Device (UID) is made of a T-shaped frame of polyethylene and burium sulphate. The vertical arm is wound with copper wine. The cooper surface a 380 mm? Two injoin threads are effacted to the lower end of the vertical arm. Dimension: 31,8 mm ± 0,2 mm wide, 31,9 mm ± 0,2 mm long.

The polyethylene traine and the wire are radio-opaque.

## Mode of action and possible effects

there are different types of intrauterine contraceptive devices. Wide-ranging international studies still verify that Copper-IUDs are not only safe but also effective over long periods. In addition, it is also generally recognized that Neo-Selfe® T CU 380 USs are one of the most effective means of contraception. Neo-Selfe® T CU 380 uSs as one of in a way to prevent initiation of the utesu. It is usually mented during mentituation. The insertion is normally pariles. The opening of the utesus is continued, the length of the uterine coality is determined, and the Neo-Selfe® T CU 380 is carefully impeted into the uterine coarty, until it is in the correct position and touches the hundus. As soon as the Neo-Safea T CU 380 has been inserted, you are protected against pregnancy.

Neo-Safe® T CU 380 is effective for five years.

ILUS are highly effective and on only be compared with the oral con-traceptive pill for the prevention of pregnancy. No contraceptive method offers 100% safety, However, in practical terms, with Neo-Safe® T.CU 380 you

It is not fully known how IUDs work. However, nowadays it is assumed It is not fully known how IADs work. However, howards is it a easured that the most probable effect is that it disrupts the normal function of the male gametes (sperm), which become incapable of fertilizing the female egg. It is also assumed that copper sons influence the development of the egg to that fertilization does not take place: IADs are no longer considered a method of abortion.

Contraindications Neo-Safe® T CU 380 should not be used in case of:

- Malignant diseases of the genital tract
- Vaginal bleeding Pregnancy

- Prespancy
   Past history of ectopic pregnancy or prediposing factors
   Infections of the genial tract
   Secually transmitted discuses during the last 12 months (except bacterial vagnitis, repeated heters infection, hepatics 8)
   Abortion with infection during the last 3 months, pelvic inflammatory
- disease (PID)
- Uterine malformations (congenital or acquired)
   Allergy to copper

The application should be reconsidered at:

- Valvular heart disease Anaemia
- Coagulation disorders
  Anti-inflammatory treatment
- Wibon's disease
- Multiple sexual partners
- Nuliperity

Possible complications and precautions
The first three cycles following insertion are usually different from your
normal cycles. Periods can be heavier, cramps and spotting may occur
both before and afterwards. Three to four cycles after insertion of the KUD menstruation normally resumes as before insertion.

Sometimes these changes are experienced between the menstrual periods

- during the cycle.
  You should contact your doctor if:
   you can not feel the threads of the IUD,
   you car your partner are able to feel the lower end of the IUD.

- you think you are pregnant, you experience abdominal pain, fever or unusual vaginal discharge, you or your partner feel pain or discomfort during sexual intercourse, your menshustion is delayed, since rarely a pregnancy outside the uterine cavity, e.g. in a fallopian tube lectopic pregnancy) may occur, you wish to have the ILO removed and / or ward to become

## Insertion and removal

Insertion and removal Before the insertion, you must be informed on the efficacy, risks and side effects of Neo-Safe® T-CU 380. A gynaecological examination including pelvic examination and a cervical smear should be performed. Pregnancy, opnital infections and sessually internatified diseases should be escluded. The position of the uterus and the size of the uterine cavity should be determined.

The instructions for insertion should be carefully taken into account and the patient card be filled out together with the attending doctor. You should return for check-up 4 to 12 weeks after insertion and once a year fi

Insertion is recommended during or shortly following menstruation. If pregnancy is excluded, Neo-Safe® T CU 380 may be inserted at any time of the cycle. It can be also inserted immediately after first trimester abortion. After having a baby, insertion should be postponed until six weeks after delivery, as this is associated with greater rates of perforation and expulsion. There are no problems about breast feeding with an IUD.

Neo-Safe® T CU 380 is removed by gently pulling on the threads. If the firreads are not visible, and the device is in the laterine cavity, removal visuals be postponed until after the next mentitual bleeding since the firreads usually become visible immediately after mentituation. If they are still not visible, the device may be removed using a narrow tenaculum. This may require dilatation of the cervical canal. After removal, pregnancy

in mediately possible. If you wish to continue using the method, a new device can be inserted at the same time. If pregnancy is not desired, the removal should be carried out during the mestbuston.

Insertion and removal may be associated with some pain and bleedings. Occasionally, the procedure may precipitate fainting or a seizure, if you suffer from epilepsy.

It is recommended that you usit your doctor for a check-up one month offer Neo-Safe\* T CU 380 was inserted to make sure the UU is still in your utenus and is positioned correctly. An annual visit is recommended thereafter. You should also check to make sure that Neo-Safe\* T CU 380 is still in your uterus by reaching up to the top of your wagns, while in a squarting position, with clean fingers to feel the threads. Do not pull on the threads.

on the threads.

If you cannot feel the threads or you can feel more of the Neo-Safe® T CU 380 than just the threads, consult your doctor immediately. This suggests that your Neo-Safe® T CU 380 is not in the uterus or is incorrectly positioned which would increase your chances of getting pregnant. It is recommended that you use an additional birth control method until you have seen your doctor. It is good practice to check that Neo-Safe® T CU 380 is in place once a month.

The available experience indicates that, in general, drugs do not interfere with the contraceptive efficacy of Neo-Safe® T CU 380 U.Ch. However, there are published reports which appear to show deminished efficacy with long-term use of non-steroidal aris-inflammatory drugs (expecially acetylaslayis) acidy and consorted with non-steroidal arti-inflammatory thugs does not appear to which contract particular articles and contract places. to reduce contraceptive efficacy.

In rare cases pain or dizoness may occur after insertion. If these complaints don't abate within half an hour of resting, the position of the IUD should be checked and the IUD may have to be removed. The IUD may rarely

## Patient card

Please complete carefully together with your physician and keep in a

The IUD is sterile and is intended for one-off use. Do not use it more

Version Date: 19Dec2018

Date of revision of the text: 11.2013

Setile

Neo-Safe® T CU 380

Manufacturer. Mona Lisa N.V. [name]

1. INTRODUCTION

This is a multi-site, participant-blinded, randomized clinical trial. The study will randomize 1000 eligible participants in a 4:1 ratio to two different copper IUDs: 800 to Mona Lisa NT Cu380 Mini and 200 to ParaGard. Recruitment will be approximately 80% nulliparous and 20% parous women, and approximately 10% of women will be \geq 36 years old.

The total duration of the study is expected to be five years. The total duration for each participant is expected to be approximately 37 months. Each woman will attend a baseline visit, followed by visits at 6 weeks, 3 months, 6 months, 12 months, 24 months and 37 months, with telephones calls at 9, 18 and 30 months. Each subject will participate for up to 37 months (or less if the product is removed or expelled). Participants will use a home pregnancy test 17 days after Exit Visit procedures or any time she suspects that she may be pregnant, and report the results to their respective sites via telephone.

The analysis plan provides additional details regarding the planned statistical analysis of the study protocol (version 2.0, 09May17). Tables, figures and listings shells will be developed and included as an appendix to a future version of the plan.

2. STUDY OBJECTIVES

The study objectives described in the protocol are as follows:

2.1. Primary Objective

To measure contraceptive efficacy of the IUD Mona Lisa NT Cu380 Mini.

2.2. Secondary Objectives

To compare between study products:

- continuation rates
- the incidence of failed IUD insertion, uterine perforation, and IUD expulsion (complete and partial)
- vaginal bleeding patterns
- pelvic pain and dysmenorrhea
- the incidence of other adverse effects
- pain with and shortly after insertion
- ease of IUD insertion
- overall product satisfaction

3. STUDY ENDPOINTS

3.1. Primary Endpoint

The primary endpoint for this study is pregnancy (contraceptive method failure).

3.2. Secondary Endpoints

- IUD continuation throughout 37 months of the study duration
- Failed IUD insertion, uterine perforation, or IUD expulsion (complete and partial)
- Vaginal bleeding patterns
- Pelvic pain and dysmenorrhea
- Other adverse effects
- Pain with and shortly after insertion
- Ease of IUD insertion
- Overall product satisfaction

4. DATA SAFETY AND EFFICACY MONITORING

An independent, autonomous Data and Safety Monitoring Board (DSMB) has been established by HD and the NIH (NICHD). The DSMB will conduct periodic reviews of study progress indicators, subject safety and pregnancy. It is expected that three (3) such reviews will occur. The Project Directors at NICHD and FHI 360 may also request additional DSMB reviews (e.g. should any other findings/issues pertaining to safety or efficacy emerge requiring DSMB review outside of the planned periodic meeting dates).

The DSMB Charter will be prepared separately by HD prior to the first DSMB meeting, and then modified as needed before subsequent meetings. The Charter will address the timing of each DSMB meeting, stopping rules relative to items including SAEs, pregnancy rates, expulsion rates, as well as detailed blinding and unblinding procedures. Additional information about the DSMB composition and review procedures will be contained in the Charter. As the primary objective of the study is non-comparative, no adjustment to confidence interval coverage error rates will be made to account for interim analyses when reporting pregnancy rate data. Similarly, no multiplicity adjustment will be made for secondary objectives.

5. ANALYSIS POPULATIONS

This analysis plan describes seven different analysis populations that are used for different purposes. The final statistical report will include an accounting of all persons screened, including the number enrolled, the number followed during the study, and other key study status indicators. The reason for excluding any data from any analysis population will be documented. The analysis population flow chart can be found in Appendix A.

The general criteria for inclusion/exclusion of participants in these seven populations are described below:

5.1. Screened Population

This population consists of all participants screened for the study, including screening failures, eligible participants not enrolled, and participants eventually enrolled.

5.2. Intent-to-treat (ITT) Population

This population includes all participants in the screened population who were enrolled and randomized. This is the most inclusive study population for analysis and includes participants who did not have a successful uterine sounding and other situations where an IUD was not inserted. Any participant who received the incorrect IUD (due to randomization or allocation error) will be included in the ITT population and analyzed as randomized. This analysis population will mainly be used for analyzing participants' baseline characteristics.

5.3. Treated Population

The Treated Population is a subset of ITT Population and includes only participants who advanced to uterine sounding, had their uterus successfully measured, and then underwent an attempted IUD insertion procedure. Inadequate uterine depth (at least 5.5cm) and/or medical contraindication (such as mucopurulent discharge discovered before/during/after sounding) are examples of situations that exclude participants from the Treated Population. Participants who received the incorrect IUD are included in this population and analyzed according to the treatment they actually received. This analysis population will mainly be used for evaluating insertion results and safety and other secondary endpoints observed during the insertion process. Participants' baseline characteristics will be analyzed only if more than 5% of the ITT Population are excluded from the Treated Population.

5.4. User Population

The User Population is a subset of Treated Population who had a successful IUD insertion. It includes participants who leave the clinic with the IUD in situ as well as those who have the product removed before leaving the clinic and exit from the study. This analysis population will mainly be used for analyzing discontinuation and safety and other secondary endpoints after a successful IUD insertion.

5.5. Per Protocol (PP) Population

This is a subset of the User population, excluding all subsequent data collected from participants with a documented protocol violation (either at baseline or during follow-up) that would prevent an accurate analysis of objectives. Participants with random allocation errors will also be excluded. This analysis population will mainly be used for sensitivity analyses of discontinuation, safety, and other secondary endpoints to evaluate the impact of protocol compliance, and only if more than 5% of the User Population are excluded from the PP Population.

5.6. Efficacy Analysis Population

The Efficacy Analysis Population is a subset of the User Population that includes women who provide at least one valid pregnancy analysis cycle as defined in Session 8.3.1. This analysis population will be used for analyzing the pregnancy endpoint. The subpopulation under 36 years old at enrollment who are in the Mona Lisa NT Cu380 Mini group and provide at least one cycle

with documented intercourse and no use of other methods will be the primary population for estimating efficacy (per FDA directives).

5.7. Lost to Follow-up Population

Lost to Follow-up Population is a subset of User Population who have the following experiences:

- left the clinic with the IUD in situ and
- had no documented IUD removal and
- whose last known use of the IUD was earlier than 37 months after IUD placement.

A subset of the Lost to Follow-up Population that has no follow-up data whatsoever is referred to as "Completely" Lost to Follow-up. Participants' baseline characteristics will be analyzed if more than 5% of the User Population are excluded from the Lost to Follow-up Population.

The following table summarizes various analyses conducted on each analysis population.

Table 1: Analyses performed on each analysis population

	Analysis						
Population				Safety and other			
1 opulation			IUD	secondary			
	Baseline	Efficacy	Discontinuation	endpoint			
Screened							
ITT	✓			✓			
Treated	√*			√ ‡			
User	✓		✓	✓			
Per protocol	✓		√ ***	√ ***			
Efficacy Analysis	✓	✓					
Lost to Follow-up	✓ **						

^{*} Analysis will be performed if > 5% of ITT Population is excluded.

^{**} Analysis will be performed if > 5% of User Population is lost to follow-up.

^{****}Analysis will be performed if > 5% of User Population is excluded.

[‡] Analysis will be performed for safety and other secondary endpoints observed during the insertion process.

The following table summarizes various study participant status included in each analysis population.

Table 2: Study participant status included in each analysis population

	Population						
Study participant status	Screened	ITT	Treated	User	Per Protocol	Efficacy	LTF
Early situations							I
Screen failures	✓						
Eligible but not enrolled	✓						
Enrolled	✓						
Protocol violation on enrollment	✓						
Post-randomization situations		•					•
Medical contraindication*		✓					
No successful sounding of the		✓					
uterus							
Uterine depth < 5.5cm		✓					
No IUD placement attempt**		✓					
Randomization errors (as		✓					
assigned)							
Randomization errors (as			✓	✓		✓	✓
treated)							
IUD placement attempts							
Attempted but failed IUD placement		✓	✓				
Successful IUD placement but		√	√	√			
immediate removal per							
request by participant							
Successful IUD placement		√	✓	√	√	√	√
and leaves clinic with IUD in							
situ							

^{*} e.g., discovering mucopurulent cervical discharge before/during/after sounding the uterus ** IUD placement attempt is defined as handling the product and attempting to place it

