# 11.4 Exit (37 months post-insertion $\pm$ 14 days) or Early Discontinuation Visit

At 37 months or at any time a participant discontinues the study, she will complete Exit Visit procedures as defined in Table 06.

During the Exit visit, collection of information on AEs, concomitant medications, IUD acceptability, and potential concerns will occur. Collection and review of diary or other contraceptive use forms (whichever form type was dispensed at previous visit) will occur with the subjects and IUD acceptability questions will be asked. Study clinicians will verify the presence of the IUD strings; if strings are not present, follow the procedures outlined in Appendix 2.

After all IUD assessments are complete, the clinician will disclose which IUD the subject was using. Those assigned to ParaGard may continue to use that product under the care of primary providers. Those assigned to the test IUD will have the product removed.

All study participants wishing to continue using a different form of contraception after the study will be referred for ongoing contraceptive care within the routine health services, including those continuing use of ParaGard. Options for continued protection from unintended pregnancies should be discussed. A short acting bridge contraceptive (condoms, 1 month of birth control pills, or 1 depo provera shot) should be provided if requested by the subject for use until referral to prevent any pregnancies occurring prior to Telephone Call 4.

Site staff will provide women with a home pregnancy test and instructions to perform the test 17 days (+ 3 days) post-removal and will be scheduled for the pregnancy test confirmation call the same day as testing. During the phone call, follow up regarding ongoing AEs, if applicable, will also be performed. If there are study related AE or new SAEs identified during the phone call, they should be followed until resolution or stabilization.

Table 06: Clinic-Based Exit Visit and Early Discontinuation Visit Procedures

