## 15 DISCONTINUATION AND REPLACEMENT OF SUBJECTS

A subject will be considered to have completed the clinical trial after she has completed 37 months of using the study product and after the final procedures have been performed.

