Appendix A: Figure 1. Analysis Population Flow Diagram

¹No IUD insertion attempt due to unable to sound the uterus prior to attempting the IUD insertion, uterus did not sound to a minimum of 5.5mm, medical conditions, or other reasons.

² Loss to Follow-up Population includes participants who provided no follow-up data (completely LTF) or who provided some follow-up data but without documented IUD removal and whose last known use of the IUD was earlier than 37 months after IUD placement.

Statistical Analysis Plan Version 3.0

REVISION HISTORY

Document	Changes	Document
Version		Date
Version 1.0	First approved version.	18APR2018
Version 2.0	Incorporated several comments from external reviewers from	14JUN2019
	NICHD and Health Decisions.	
	1. Included menstrual hygiene product used by the	
	participant into IUD expulsion analysis.	
	2. Added analysis section for STI/RTIs assessment	
	results during the study period.	
Version 3.0	The self-imposed blinding is no longer necessary and	08OOCT2019
	therefore, has been removed.

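### The SAP's Lost to Follow-up rule, read literally, counts ParaGard users who attend Exit shortly before month 37 and keep the device as lost, with no counterpart in the Mini arm

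*SAP*

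**What the plan says.** SAP 5.7 defines the Lost to Follow-up Population as the User Population members who meet three conditions:

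1. "left the clinic with the IUD in situ and"
2. "had no documented IUD removal and"
3. "whose last known use of the IUD was earlier than 37 months after IUD placement"

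SAP Appendix A, footnote 2, repeats the rule for women with some follow-up data: "without documented IUD removal and whose last known use of the IUD was earlier than 37 months after IUD placement". Neither place mentions a visit window or whether the woman attended Exit.

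Protocol 11.4 sets the Exit visit at 37 months plus or minus 14 days and treats the arms differently at that visit. For the control: "Those assigned to ParaGard may continue to use that product under the care of primary providers". For the test device: "Those assigned to the test IUD will have the product removed". Appendix 1, note 10, says the same.

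The population is used in two places. SAP 7.1 tabulates the number and percentage in each analysis population by treatment. SAP Table 1 calls for a baseline summary of the lost women if more than 5% of the User Population is lost.

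**The concern.** A woman who attends her scheduled Exit visit has been followed to the end of the study, whether or not she keeps the device. The SAP rule identifies loss from the absence of a removal record combined with a date short of exactly 37 months. That combination also describes a ParaGard user who comes to Exit a week early, within the allowed window, and keeps her IUD. It cannot describe a Mini user at the same visit, because her removal is on record.

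The set of lost women would therefore be inflated in the control arm only. Its baseline table would mix women who were really lost with women who stayed to the end. The same woman could appear as having completed in the End of Trial table and as lost in the analysis-population table of the same section. Loss by arm is a basic measure of trial credibility, and a spurious one-sided excess invites an attrition concern that the data do not warrant.

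**Working it through.** **Applying the rule.** Taking 30.4375 days per month, the Exit window runs from 37 − 14/30.4375 = 36.54 to 37 + 14/30.4375 = 37.46 months.

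| Woman at Exit, 1 to 14 days before month 37 | Left clinic with IUD | No documented removal | Last known use before 37 months | Counted as lost |
|---|---|---|---|---|
| ParaGard, keeps device | yes | yes | yes | yes |
| ParaGard, device removed | yes | no | yes | no |
| Mini, device removed | yes | no | yes | no |

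**Does later contact repair it?** Call 4 comes 17 days after Exit. For an Exit on day −14 that is day −14 + 17 = +3, after month 37. But Protocol 11.5 collects only the pregnancy test result and adverse events at that call, and Appendix 1 marks no IUD continuation or placement item there. Nothing scheduled clearly moves last known use past the Exit date.

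**Size.** Mislabelled women = ParaGard women × continuation to Exit × share keeping the device × share exiting before month 37.

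Inputs:
- ParaGard women: about 220 of 1100 (Protocol 4.1). The SAP introduction still has 200 of 1000; the percentages are the same at 4:1.
- Continuation: not stated for ParaGard at month 37. Protocol Table 09 gives 51.2% for the Mini arm. This is 0.8³ = 0.512, strictly the 36-month value; 0.8^(37/12) = 0.503. For a low value, the 70% 12-month ParaGard figure in Protocol 19.1, held constant, gives 0.70^(37/12) = 0.333. For a high value, the event rates in Table 2 of the ParaGard label (Protocol Appendix 7) sum to 20.8, 14.7 and 10.8 per 100 in years 1 to 3, giving 0.792 × 0.853 × 0.892 = 0.60 before personal removals. Range used: 33% to 60%.
- Share keeping the device: assumed 50% to 90%; not in the documents.
- Share exiting early: assumed 30% to 50%; not in the documents.

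| Case | Product | ParaGard women | % of arm | % of 1100 |
|---|---|---|---|---|
| Low | 0.333 × 0.5 × 0.3 = 0.050 | 11 | 5% | 1.0% |
| Middle | 0.512 × 0.7 × 0.5 = 0.179 | 39 | 18% | 3.6% |
| 51.2% continuation, other two at maximum | 0.512 × 0.9 × 0.5 = 0.230 | 51 | 23% | 4.6% |
| High | 0.60 × 0.9 × 0.5 = 0.270 | 59 | 27% | 5.4% |

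The Mini count by this route is 0 in every case.

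**The 5% trigger.** Its denominator is the whole User Population, at most about 1100 women, so it needs about 0.05 × 1100 = 55. That is 55/220 = 25% of the ParaGard arm. With the other two shares at their assumed maxima (0.9 × 0.5 = 0.45), continuation would have to reach 0.25/0.45 = 56%.

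**What it touches.**
- The primary analysis is in Mini users only (SAP 7.3).
- Discontinuation estimates and logrank tests stop at 36 months (SAP 7.4.2), before the window opens at 36.54 months.
- End-of-study status and its between-arm test come from the End of Trial form (SAP 7.1).

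**The case against.** The strongest reply is that the trial has a sound measure of loss elsewhere. SAP 7.1 takes end-of-study status from the End of Trial form, and SAP 7.4.1 lists completion and loss to follow-up as separate reasons. Protocol 15.1.1 requires at least three documented contact attempts before a woman is called lost, so a woman who attends Exit would not be recorded as lost there. This stands. A reader might infer that the trial's reported disposition would show a large false loss in the control arm; the documents do not support that. Only the SAP 5.7 headcount and one conditional baseline table are wrong.

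A reader might also infer that the artefact would set off the 5% trigger. On the ranges above it does so alone only near the top corner. It could add to real losses: Protocol 19.1 allows for up to 5% lost, and near that level a few extra women would tip it. The consequence would be one extra descriptive table.

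Two further replies carry less weight. First, the SAP does not define last known use, and Appendix 1 places the final status form at Call 4, so that contact might be taken as the date. This is possible but unsettled, since no IUD-status item is scheduled then. Second, Protocol 15 counts a woman as complete only "after she has completed 37 months of using the study product and after the final procedures have been performed", with no window, so an early in-window exit is not strictly a completer. That shows the same missing window in the protocol; it does not make a woman who attended Exit lost.

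**Conclusion.** The point holds as a definition that gives the wrong answer when followed exactly, confined to a descriptive population. On assumed ranges of 33% to 60% ParaGard continuation, 50% to 90% keeping the device and 30% to 50% exiting early, about 11 to 59 of 220 ParaGard women would be placed among the lost, and no Mini women by this route. Two of those three shares have no source in the documents. More extreme values give more: 51.2% continuation, all keeping the device and 75% exiting early gives 0.384 × 220 = 84 women, or 7.7% of 1100.

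The artefact could contribute to the 5% trigger but would rarely fire it alone. No efficacy or discontinuation result is affected. The one-arm pattern also depends on the current protocol: Protocol 4.1 contemplates later continued use of the Mini under separate consent, which would carry the same error into that arm.

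**What to change.** Preferred: define the Lost to Follow-up Population as User Population members whose End of Trial status is Lost to Follow-up. This matches the disposition table in SAP 7.1 and needs no date cut-off.

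Alternative: keep the three conditions and add a fourth, that the woman did not complete the final Exit visit. Do not tie this to the 14-day window, because a ParaGard user who attends Exit on day −15 and keeps the device would still be labelled lost.

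Make the same change in Appendix A footnote 2. The cost is one sentence in SAP 5.7 and one in the footnote. No new data are needed, since End of Trial status is already collected.
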